This is a multi-center, randomized, double-blind, bismuth-containing quadruple active comparator-controlled Phase 3 clinical study to evaluate the efficacy and safety of Rifasutenizol (RSZ, formally known as TNP-2198) in combination with rabeprazole and amoxicillin in treatment-naïve participants with H. pylori infection using an adaptive design with sample size re-estimation. The status of H. pylori infection during the Screening Period is determined by ¹³C-urea breath test (¹³C-UBT) and confirmed by gastroscopic biopsy histology.

Eligible subjects will be randomly assigned to test group or control group at a 1:1 ratio stratified by study site, and will receive RSZ capsules, rabeprazole sodium enteric-coated tablets, amoxicillin capsules combined with clarithromycin placebo tablets and bismuth potassium citrate placebo capsules (test group), or bismuth-containing quadruple regimen of amoxicillin capsules, clarithromycin tablets, rabeprazole sodium enteric-coated tablets and bismuth potassium citrate capsules combined with RSZ placebo capsules (control group) for 14 consecutive days. ¹³C-UBT will be performed 4-6 weeks after the last dose to evaluate the eradication effect of H. pylori.

This study will also conduct a PK study at one study site to evaluate the PK profile of RSZ when administered in combination with rabeprazole and amoxicillin. A minimum of 20 subjects and a maximum of 40 subjects will be enrolled in the PK study at this study site, and randomly assigned to the test group and the control group in a 1:1 ratio. For the enrolled subjects, PK blood samples will be collected before and after the morning administration on Day 1 (D1) and D14 (1-3 day(s) earlier if necessary).

Number of Subjects

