According to the study results of clinical trials for H. pylori eradication in China and abroad, it is estimated that the eradication rate of H. pylori with 14-day bismuth-containing quadruple therapy (amoxicillin, clarithromycin, rabeprazole and bismuth potassium citrate) is about 85%. If the eradication rates of H. pylori in the test group and the control group are both 85%, Type I error is 0.025 (one-sided), power is 90%, a non-inferiority margin is -10%, and a dropout rate is about 15%, the required sample size is about 700 subjects (350 and 350 subjects in the test group and the control group, respectively, including the subjects participating in the PK study). Considering the uncertainty of the treatment effect, an adaptive design with sample size re-estimation is planned in this trial. One interim analysis is planned will be performed by an independent data monitoring committee (IDMC) when the primary endpoint data of 50% of the subjects are obtained. If the eradication rate of H. pylori observed in the test group is less than 10% in the control group, the trial can be terminated due to futility. In addition, sample size re-estimation will be performed during the interim analysis, and the re-estimation of sample size will be based on the Promising-Zone method (2011). The actual sample size will depend on the effect size or p-value observed during the interim analysis. Up to 1200 subjects are planned to be enrolled in this study. If the eradication rate of H. pylori in the test group 4-6 weeks after the end of treatment is non-inferior to that in the control group, the superiority comparison between the test group and the control group will be further performed.

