Efficacy analysis is mainly based on the test results of ¹³C-UBT at 4-6 weeks after the last dose of study drugs to evaluate the effect of H. pylori eradication. Analysis will be mainly based on mITT set, and sensitivity analysis or supplementary analysis will be performed for the primary endpoints based on other efficacy analysis sets (ITT, Micro-ITT, and PP). Descriptive analysis is performed using frequency (percentage) according to ¹³C-UBT test results (negative or positive) in different groups. Farrington-Manning test is used as the primary analysis for non-inferiority comparison between the test group and the control group, with non-inferiority margin of -10%; If the non-inferiority test is statistically significant, the Farrington-Manning method is continued to be used for superiority test (null hypothesis is that the difference in eradication rate of H. pylori between the test group and the control group is ≤ 0 , and alternative hypothesis is that the difference in eradication rate of H. pylori between the test group and the control group is > 0). As a supportive analysis, the point estimate and two-sided 95% confidence interval (CI) of the difference in eradication rate of H. pylori between the test group and the control group will be calculated using the Miettinen-Nurminen method. If the lower limit of the 95% CI is greater than -10%, the eradication rate of H. pylori in the test group is considered to be non-inferior to that in the control group. If the test group is noninferior to the control group and the lower limit of 95% CI is > 0, the eradication rate of H. pylori in the test group is considered superior to that in the control group. In addition, the efficacy of RSZ in combination with rabeprazole and amoxicillin in treatment-naïve participants with H. pylori infection is evaluated in a subgroup analysis based on the results of H. pylori culture and drug susceptibility testing.

Safety analysis

The evaluation and analysis of safety and tolerability are mainly based on descriptive statistics. Aes, treatment-emergent adverse events (TEAE), serious adverse events (SAE), drug-related TEAE, and TEAE leading to withdrawal from the trial will be summarized.

The number and incidence of TEAE will be summarized and described by system organ class and preferred term in each group.

The number and incidence of TEAE will be summarized and described by system organ class, preferred term, and severity in each group.

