The number and incidence of drug-related TEAE will be summarized and described by system organ class and preferred term in each group.

Vital signs (blood pressure, respiration, pulse, and body temperature), laboratory tests and ECG results and changes from baseline will be summarized and described in each group, and clinically significant abnormal results and all test results post-baseline will be listed.

SAE, TEAE leading to discontinuation of study treatment, and TEAE leading to premature withdrawal from the study will be presented separately.

Pharmacokinetic analysis

Pharmacokinetic parameters (non-compartmental models) will be estimated and analyzed for plasma concentration data using Phoenix WinNonlin software, and the main pharmacokinetic parameters will be calculated using PKPS data.

PK concentration data will be statistically summarized and tabulated for RSZ at each sampling time point as defined in the protocol. Mean and median drug concentration-time profiles (linear and semi-logarithmic plots) will also be plotted by planned sampling time for each subject. The PK concentration data for individual subjects will be used to plot the drug concentration-time curve (linear and semi-logarithmic plots) based on the actual sampling time.

For samples with concentrations below the quantification limit, samples sampled before C_{max} should be calculated as zero and samples sampled after C_{max} should be calculated as not detectable when performing pharmacokinetic analysis. According to the treatment groups, the analysis results of main pharmacokinetic parameters are summarized and displayed by sample size, arithmetic mean, standard deviation, coefficient of variation, median, minimum, maximum, geometric mean, and geometric coefficient of variation.

PK parameters of the first dose include: T_{max} , C_{max} , $t_{1/2}$, AUC_{0-tau} , $AUC_{0-\infty}$, Vd/F, and CL/F. PK parameters of the multiple-dose include: T_{max} , ss; C_{max} , ss; $t_{1/2}$, ss; AUC_{0-tau} , ss; $AUC_{0-\infty}$, ss; Vd/F_{ss} ; CL/F_{ss} ; and R_{ac} . For subjects with $AUC_{-\% Extrap} > 20\%$, descriptive statistical analysis will not be performed for $AUC_{0-\infty}$, $t_{1/2}$, CL/F, Vd/F, and $AUC_{-\% Extrap}$.

The statistical analysis method and plan are detailed in the statistical analysis plan.

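### Randomisation is stratified by site, but the described Farrington-Manning tests and Miettinen-Nurminen interval are not: valid, but mildly conservative if sites differ

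*Combined protocol and SAP*

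**What the plan says.** Under Methodology/Study Design, subjects are "randomly assigned to test group or control group at a 1:1 ratio stratified by study site". No other stratification factor is named.

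Under Statistical Method, Efficacy analysis, "Farrington-Manning test is used as the primary analysis for non-inferiority comparison between the test group and the control group", with a margin of -10%. If that succeeds, "the Farrington-Manning method is continued to be used for superiority test", against a null difference of zero or less. The supportive difference and its two-sided 95% interval "will be calculated using the Miettinen-Nurminen method". All three are described as comparisons of two groups, with no site term, site weights or pooling rule. The sensitivity and supplementary analyses change only the analysis set (ITT, Micro-ITT, PP).

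The Statistical Method section closes with "The statistical analysis method and plan are detailed in the statistical analysis plan". The text of that plan is not in the public document.

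Under Number of Subjects, one interim analysis takes place "when the primary endpoint data of 50% of the subjects are obtained". It can raise the sample size from about 700: "Up to 1200 subjects are planned to be enrolled in this study". Stated superiority power is about 78% for 90% against 83%, and about 66.1% for 90% against 84%.

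**The concern.** With 1:1 allocation balanced within each site, a site with high or low eradication affects both arms equally, so differences between sites drop out of the treatment difference. An unstratified test still estimates its variance from the pooled rate, p(1 - p), which includes the between-site variance. The standard error is then somewhat too large, the actual one-sided level falls below 2.5%, and some precision already provided by the randomisation goes unused.

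Superiority is where this matters most, because its stated power is 78% or less. There is also a matter of definition. The interim resizing uses the observed effect size or p-value, so the statistic should be fixed in advance and be the same at the interim and final analyses.

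**Working it through.** **Inputs from the synopsis.** 85% eradication in both arms, one-sided level 0.025, 90% power, margin -10 points, 15% dropout, about 700 subjects (350 per arm), cap 1200.

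**Inputs assumed.** The number of sites and the between-site spread are not stated. The main runs use 35 equal sites and site SDs of 0, 5 and 10 points. An SD of 10 puts 95% of sites between 59% and 97%, which is a strong spread.

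**The plan's sample size.** With null difference -0.10 and 85% in both arms, the Farrington-Manning restricted rates are 0.787 and 0.887.
- n = [1.960 × √(0.787×0.213 + 0.887×0.113) + 1.282 × √(2×0.85×0.15)]² / 0.10² = 276 per arm.
- A continuity correction gives 296. Dividing by 0.85 gives 349 per arm, or 698 in total, in agreement with about 700.
- Without the correction, which the synopsis does not mention, the total is 650. Nothing below depends on this.

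**Variance and level at the superiority null (85/85).** Within-site variance = p(1 - p) - SD², and the actual level = 1 - Φ(1.96 × SE ratio).
- SD 5: 0.1275 - 0.0025 = 0.1250. SE ratio √(0.1275/0.1250) = 1.010. Level 2.39%.
- SD 10: 0.1275 - 0.0100 = 0.1175. SE ratio √(0.1275/0.1175) = 1.042. Level 2.06%.

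**Simulation.** Site effects were normal on the logit scale (SD 0.39 and 0.80, giving 5 and 10 points). The unstratified Farrington-Manning test was compared with a stratified Miettinen-Nurminen score test using Mantel-Haenszel weights. There were 160,000 runs for levels, 80,000 for superiority power and 40,000 for non-inferiority power. Entries are unstratified / stratified, in %.

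| Quantity | SD 0 | SD 5 | SD 10 |
|---|---|---|---|
| Level, 85/85, N = 700 | 2.56 / 2.53 | 2.50 / 2.58 | 2.09 / 2.48 |
| Superiority power, 90/83, N = 700 | 78.2 / 78.0 | 78.2 / 78.5 | 78.5 / 80.0 |
| Superiority power, 90/84, N = 700 | – | 66.0 / 66.3 | 66.7 / 68.7 |
| Non-inferiority power, 85/85, N = 700 | – | 95.9 / 96.0 | 96.3 / 96.6 |
| Non-inferiority power, 82/85, N = 700 | 70.3 / 70.3 | 69.9 / 70.3 | 71.0 / 72.6 |
| Superiority power, 90/83, N = 1190 | – | 94.6 / 94.7 | 94.6 / 95.2 |

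Repeat simulations of the same comparison gave superiority gaps of 0.3 to 0.4 points at SD 5 and 1.8 to 2.3 at SD 10. Unequal sites with incomplete blocks of four gave 0.3 and 1.7 at 90/83.

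**After dropout.** At 297 per arm (350 × 0.85), the formula gives non-inferiority power of 92.2% unstratified and 92.5% stratified at SD 5, and 92.8% and 93.9% at SD 10.

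**Sparse sites at the interim.** With 5 per arm per site, the chance that a site has no failure in either arm is 0.85¹⁰ = 19.7% if sites do not differ. By simulation it is 22.5% at SD 5 and 29.5% at SD 10.

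**The -10% null (75/85) at SD 10, unstratified / stratified score.**
- Constant risk difference across sites: 2.11 / 2.41% (N = 700) and 2.18 / 2.51% (N = 1190).
- Constant shift on the logit scale, sites redrawn each run: 2.38 / 2.74% and 2.64 / 3.01%.
- The simpler Mantel-Haenszel/Sato version under the same logit shift: 2.99% (35 sites × 10 per arm) and 3.28% (20 sites × 17 per arm).

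**The case against.** The strongest objection is that the remedy may worsen the test that matters most. Non-inferiority is the primary objective and the plan promises strict error control. Yet at the -10% null, with strong site spread and a constant logit effect, the stratified score test reaches 2.7% to 3.0%, above the unstratified test. That is also the only spread at which the power gain exceeds half a point.

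This stands as a caution. The excess appears when sites are redrawn at random, so that the average difference over the enrolled sites moves around -10 points. With the sites held fixed and their average difference exactly -10 points, the stratified score test runs at about 2.3 to 2.4% and the unstratified test at about 2.0%. The null should still be checked in the sponsor's own simulations.

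A second objection is that this is a synopsis, that both named methods exist in stratified form, and that the SAP may already settle the matter. That is correct, and it limits the point to what is described here. A third is that the benefit to non-inferiority is negligible at moderate spread and that nothing in the document supports an SD of 10 points. That also stands, and it is why the point is minor.

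**Conclusion.** The concern holds, as a minor one. The described analysis does not use the only stated stratification factor. Leaving it out does not inflate type I error, and no figure in the plan is wrong because of it. At N = 700 the cost in superiority power is about 0.3 to 0.5 points at site SD 5 and about 1.5 to 2 points at site SD 10. For non-inferiority at 85/85 it is 0.1 to 0.3 points at SD 5 and 0.3 to 1.0 at SD 10, across the two sample sizes examined. If sites do not differ there is nothing to gain.

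These figures rest on assumed site numbers and spreads. Fixed sizes of 700 and 1190 bracket the final size. The re-estimation rule was not modelled, so the statement about type I error concerns stratification only and not the adaptive design. Confidence is medium, because the SAP may already specify a stratified analysis.

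**What to change.** Before unblinding, specify a site-stratified risk difference in the SAP: the stratified Miettinen-Nurminen/Farrington-Manning score form with Mantel-Haenszel weights, for the -10% null, the zero null and the 95% interval. Prefer the score form to the Mantel-Haenszel/Sato version, given the levels above. Pre-specify how small sites are pooled, use one statistic at the interim and final analyses, and keep the unstratified Farrington-Manning test as a sensitivity analysis.

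If the sponsor prefers the unstratified test as primary, the SAP should say so explicitly and add the stratified test as a pre-specified sensitivity analysis.

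Neither option needs more subjects. Making the stratified test primary costs SAP wording, the pooling rule, a rerun of the adaptive-design simulations that includes the -10% null, and about 0.2 points of power if sites turn out not to differ.

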Pharmacokinetic parameter set (PKPS): includes all randomized subjects who have received RSZ capsules and have at least one valid PK parameter data and will be analyzed according to actual treatment groups.

Efficacy Evaluation

Efficacy analysis and estimands:

The efficacy endpoint of the study is the eradication rate of H. pylori 4-6 weeks after the last dose of the study drug, and the analysis of the mITT population is the primary analysis of the study.

Depending on the study objectives and study design, the following primary estimands are specified:

	Primary estimand
Population	Treatment-naïve participants with H. pylori infection who meet the inclusion and exclusion criteria
Variable	Eradication of H. pylori (based on the test results of ¹³ C-UBT) 4-6 weeks after the end of treatment
Treatment	RSZ capsules (400 mg) administered BID in combination with rabeprazole sodium enteric-coated tablets (20 mg), amoxicillin capsules (1 g), clarithromycin placebo tablets, and bismuth potassium citrate placebo capsules, or bismuth-containing quadruple regimen plus RSZ placebo capsules; Continuous treatment for 14 days
Intercurrent events	Intercurrent events affecting the assessment of the primary endpoint include, but are not limited to:
	Discontinuation of study treatment
	• Events of concomitant medications and non-drug therapy during the study that may affect the test results of the post-treatment ¹³ C-UBT
	Detailed descriptions of intercurrent events, missing data, related to the estimands will be provided in the statistical analysis plan.
Population level summary	Eradication rate of H. pylori at 4-6 weeks after the end of treatment in the test group and the control group

In addition, subgroup analysis of efficacy endpoints will also be performed based on drug susceptibility testing results: based on the baseline H. pylori culture and drug susceptibility testing results, the patients will be grouped according to the resistance status (resistant or sensitive) to rifabutin, amoxicillin, clarithromycin, metronidazole, tetracycline, furazolidone and levofloxacin, and the eradication rates of H. pylori at 4-6 weeks after the last dose of the test group and the control group in each subgroup will be analyzed.

Safety Evaluation

Safety endpoints: incidence of adverse events (AEs) during the study, relationship with the study drugs and severity, laboratory tests (hematology, urinalysis, blood chemistry), vital signs, ECG, physical examination.

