Pharmacokinetics (PK)

For subjects participating in the PK study, PK blood samples (4 mL each) will be collected in the ethylenediamine tetraacetic acid (EDTA) anticoagulant tubes within 30 minutes before the first study drugs administration in the morning and 1, 2, 3, 4, 5, 6, 7, 8, 10, and 12 hours (before the second RSZ capsules/placebo administration on the same day) after RSZ capsules/placebo administration on D1 and D14 (1-3 day(s) earlier if necessary). The allowable time window for blood sampling is \pm 0. 5 hours.

- PK parameters of the first dose include: T_{max}, C_{max}, t_{1/2}, AUC_{0-tau}, AUC_{0-∞}, Vd/F, and CL/F.
- PK parameters of the multiple-dose include: T_{max, ss}; C_{max, ss}; t_{1/2, ss}; AUC0_{-tau, ss}; AUC0_{-∞, ss}; Vd/F_{ss}; CL/F_{ss}; and R_{ac}.

Statistical Method

Demographical analysis

Demographic analysis is conducted based on the ITT. Descriptive statistics will be performed for all demographic (age, sex, weight, height, ethnicity, etc.) and baseline characteristics, taking the last valid measurement before the administration of the study drugs as the baseline.

Efficacy analysis

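### The 20% extrapolation rule removes AUC_%Extrap from its own summary, capping it at 20%; it may also shorten first-dose t1/2, depending on a half-life the documents do not give

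*Combined protocol and SAP*

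**What the plan says.** Synopsis, Statistical Method, Pharmacokinetic analysis: once a subject's AUC_%Extrap passes 20%, "descriptive statistical analysis will not be performed for" five quantities: AUC0-∞, t1/2, CL/F, Vd/F and AUC_%Extrap. The main parameters are otherwise "summarized and displayed by sample size, arithmetic mean, standard deviation" and further statistics, including the maximum. AUC_%Extrap is not among the listed PK parameters, but naming it in the exclusion implies that it is summarised for the other subjects. The same section also plans that "PK concentration data will be statistically summarized and tabulated for RSZ at each sampling time point", with individual linear and semi-logarithmic curves.

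Synopsis, Pharmacokinetics (PK): the last sample is at "12 hours (before the second RSZ capsules/placebo administration on the same day"; the schedule runs "after RSZ capsules/placebo administration on D1 and D14 (1-3 day(s) earlier if necessary".

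Synopsis, Methodology/Study Design: "A minimum of 20 subjects and a maximum of 40 subjects will be enrolled in the PK study", randomised 1:1, so about 10 to 20 receive RSZ. The PK parameter set (PKPS) "includes all randomized subjects who have received RSZ capsules and have at least one valid PK parameter data".

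**The concern.** Withholding AUC0-∞, CL/F and Vd/F when too much of the area is extrapolated has a sound rationale, because those values depend on the extrapolation. The rationale does not carry over to AUC_%Extrap, which is the diagnostic that says whether the other values can be trusted. If it is summarised only where it passed, the summary shows a pass.

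There is a second, weaker consequence. With sampling fixed at 12 h, the extrapolated share rises with half-life. A rule that drops subjects with a high share therefore tends to drop those with long half-lives, and first-dose t1/2, a named secondary PK parameter, may read short.

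What is at stake is the reading of a descriptive PK table in 10 to 20 subjects. No test or decision hangs on it.

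**Working it through.** The plan states no figure to reproduce here. The documents supply the 20% threshold, the 12 h last sample, the 12 h dosing interval and the 10 to 20 RSZ subjects. They give no half-life, between-subject variability or absorption rate for RSZ. Those are assumed below and shown as a range.

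**1. The cap.** If only values of 20% or less are summarised, the maximum cannot exceed 20%. This follows from the wording alone.

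**2. The half-life at which the rule starts to act after the first dose.**
- Mono-exponential decline: extrapolated share = exp(-12k), with k = ln2/t1/2. Setting this to 0.20 gives t1/2 = 12 × ln2/ln5 = 5.17 h.
- One-compartment oral model: share = [ka·exp(-12k) - k·exp(-12ka)]/(ka - k). Setting this to 0.20 gives 4.13, 4.70 and 4.94 h for ka = 0.5, 1 and 2 per h.

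**3. What the rule would remove.** Assume log-normal half-lives with CV 30%, so s = √ln(1.09) = 0.294, and ka = 1/h, so the cut-off is 4.70 h. With z = ln(4.70/median)/s, the dropped fraction is 1 - Φ(z), and the ratio of kept to true mean t1/2 is Φ(z - s)/Φ(z). For a 4 h median, z = 0.549, Φ(z) = 0.709 and Φ(z - s) = 0.601. So 29% are dropped and the ratio is 0.601/0.709 = 0.85. The AUC_%Extrap rows come from simulation under the same model.

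| Assumed median t1/2 | 2 h | 3 h | 4 h | 5 h |
|---|---|---|---|---|
| Expected number above 20%, of 10 | 0.0 | 0.6 | 2.9 | 5.8 |
| Chance of at least one in 10 | 2% | 48% | 97% | 100% |
| Expected largest AUC_%Extrap of 10, all subjects | 10% | 20% | 30% | 38% |
| Expected largest, as summarised | 9% | 16% | 18% | 18% |
| Mean AUC_%Extrap, all subjects | 3.4% | 9.3% | 16.2% | 22.7% |
| Mean AUC_%Extrap, as summarised | 3.3% | 8.3% | 12.0% | 14.1% |
| Bias in mean first-dose t1/2 | 0% | -5% | -15% | -26% |
| Bias in median first-dose t1/2 | 0% | -2% | -10% | -21% |

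Over CV 20 to 40% and cut-offs of 4.13 to 5.17 h, the bias in mean t1/2 runs from -4% to -28% at a 4 h median and from 0 to -4% at a 2 h median.

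**4. Check with simulated non-compartmental analysis.** Profiles were generated at the planned sampling times with variable absorption and 10% assay error. Mean t1/2 bias under the rule was +1.9, -5.0, -16.7 and -28.3% at medians of 2, 3, 4 and 5 h. Keeping every subject gave +2.8, +2.5, +3.5 and +4.7%, and 0% to +10% over ka of 0.7 to 2 per h.

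**5. What other outputs recover.** With linear, time-invariant PK and a 12 h interval, AUC0-tau,ss equals first-dose AUC0-∞. The extrapolated share is then 1 - AUC0-tau/AUC0-tau,ss, and 20% corresponds to an AUC-based accumulation ratio of 1/(1 - 0.20) = 1.25. In simulated groups of 10 subjects, this ratio gave mean shares of 3.5, 9.6, 16.5 and 23.1%, against true values of 3.5, 9.5, 16.4 and 22.9%.

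**The case against.** The best counter-argument is that the information is not lost. Sample size is displayed with each parameter, so the fall in n from AUC0-tau to AUC0-∞ shows how many subjects were dropped. Concentrations at 12 h and the individual semi-logarithmic curves keep everyone. AUC0-tau, AUC0-tau,ss and R_ac are not on the exclusion list and, as step 5 shows, can give back the extrapolated share. The rule withholds descriptive statistics only and does not bar individual listings. AUC_%Extrap is not an endpoint, and the section refers further detail to the statistical analysis plan.

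Much of this stands. A reader might infer that no planned output shows the size of the excess, or that the PK tables will look acceptable whatever happened; the documents do not support either reading. The recovery is indirect, however. It needs PK that is linear and stationary over 14 days, and the documents do not define R_ac. None of it explains why the diagnostic should be left out of its own summary.

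A reader might also infer that first-dose t1/2 will be biased. That is not shown. The cut is on AUC_%Extrap, not on t1/2, so with variable absorption it is soft, and with a half-life near 2 h it has almost no effect.

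**Conclusion.** The point holds as a minor one. The cap on the AUC_%Extrap summary is certain and needs no assumption. Its practical effect depends on the half-life. At an assumed 4 or 5 h median, the expected reported maximum among 10 subjects is about 18%, against 30 or 38% as it occurred. At 2 h there is almost no difference.

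The shortening of first-dose t1/2 is a conditional risk: negligible at about 2 h, about -15% in the mean at 4 h and -26% at 5 h. These figures rest on a one-compartment model with ka 1/h and CV 30%, all assumed.

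The rule's parameter names carry no steady-state suffix, so it reads as first-dose only, but the text does not say whether D14 is covered. A reader might count this as an error. It is only missing detail, which the statistical analysis plan may settle, and it is not part of this point. Cmax, Tmax, AUC0-tau and the efficacy analysis are unaffected.

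**What to change.** Take AUC_%Extrap off the exclusion list. Summarise it for all PKPS subjects with an estimable value and report the number above 20%. Keep the 20% rule for AUC0-∞, CL/F and Vd/F.

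Optionally, add a supportive first-dose t1/2 row that includes the flagged subjects. Its footnote should say that their values are less reliable and that the all-subject mean may be slightly long (0% to +10% in the simulation).

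The cost is one or two table rows and a footnote, with no new samples.
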